7. STUDY ASSESSMENTS AND PROCEDURES

Protocol waivers or exemptions are not allowed with the exception of immediate safety concerns. Therefore, adherence to the study design requirements, including those specified in the Time and Events Table, are essential and required for study conduct.

This section lists the procedures and parameters of each planned study assessment. The exact timing of each assessment is listed in the Time and Events Table in Section 7.1.

The following points must be noted:

- If assessments are scheduled for the same nominal time, THEN the assessments are recommended to occur in the following order:
 1. 12-lead ECG
 2. vital signs
 3. blood draws

Note: The timing of the assessments should allow the blood draw to occur at the exact nominal time.

- The timing and number of planned study assessments, including safety, pharmacokinetic, pharmacodynamic, immunogenic or other assessments may be altered during the course of the study based on newly available data (e.g., to obtain data closer to the time of peak plasma concentrations) to ensure appropriate monitoring.
- The change in timing or addition of time points for any planned study assessments must be documented in a Note to File which is approved by the relevant GSK study team member and then archived in the study sponsor and site study files, but this will not constitute a protocol amendment.
- The Institutional Review Board (IRB)/ Independent Ethics Committee (IEC) will be informed of any safety issues that require alteration of the safety monitoring scheme or amendment of the Informed Consent Form.
- No more than 500 mL of blood will be collected over the duration of the study, including any extra assessments that may be required.

7.1. Time and Events Table**7.1.1. Time and Events Table – General Overview****Group 1**

Procedure	Study Day			
	Screening ⁴	Main Phase	Follow – Up 1 (approx. 24 hours post dose)	Follow – Up 2 (7-14 days post dose)
Informed Consent and Demography	X			
Brief Physical Examination	X			
Medical history (incl. substance abuse)	X			
Inhaler device training / education session	X			
Laboratory assessments ¹	X			
Vital signs ²	X	X		
Pharmacokinetic blood sample		X		
Oxytocin Administration (IM/IH)		X		
Full blood count		X		
Labour Events Documentation		X		
Device acceptability questionnaire ³		X		
Prior / concomitant medication review	X	X	X	X
AE review		----- continuous review -----		
SAE review		----- continuous review -----		

1. Only required if done as part of routine care. Additional study-specific laboratory assessments not required.
2. Includes blood pressure, heart rate, temperature, respiratory rate
3. Only to be used when randomized to IH oxytocin
4. To be completed after 18th week of pregnancy (based on estimated date of delivery).

Group 2

Procedure	Study Day		
	Screening ⁵	Main Phase	Follow - Up (7-21 days post dose)
Informed Consent and Demography	X		
Brief Physical Examination	X	X	
Medical history	X		
Pregnancy test	X	X	
Alcohol Breath Test, Smokerlyzer, Urine Drug Screen ¹	X	X	
HIV, Hep B and Hep C screen ²	X		
Inhaler device training / education session	X		
Laboratory assessments (including liver chemistries)	X	X	
Immunogenicity sample		X	X
12-lead ECG	X ⁴	X	
Cardiac Telemetry		X	
Vital signs ³	X	X	
Spirometry (FEV-1) ⁴	X	X	
Admission to unit		X	
Pharmacokinetic blood sample	X	X	
Oxytocin Administration (IH or IV)		X	
Prior / concomitant medication review	X	X	X
AE review		----- continuous review -----	
SAE review	----- continuous review -----		
Discharge from unit		X	

1. Smokerlyzer at PI/designee discretion if smoking history in question.
2. If test otherwise performed within 3 months prior to first dose of study treatment, repeat testing at screening is not required.
3. Includes blood pressure, heart rate, temperature, respiratory rate, and SpO2.
4. Performed in triplicate.
5. To be completed within 28 days of randomization.

7.1.2. Time and Events – Main Phase Procedures**Group 1**

Procedure	Pre-dose	Time post dose										
		3 min	5 min	10 min	15 min	20 min	30 min	1 hr	2 hr	2.5 hr	3 hr	4 hr
Vital signs ¹							X		X			
Pharmacokinetic blood sample	X ²	X	X	X	X	X	X	X	X	X	X	X
Prior medication review	X											
Concomitant medication review		----- continuous review -----										
AE review		----- continuous review -----										
SAE Review		----- continuous review -----										
Device Acceptability Questionnaire ³												X
Full Blood Count	X											X

1. Includes blood pressure, heart rate, temperature, respiratory rate
2. Predose PK sample to be taken immediately prior to administration of study treatment
3. Only to be administered when randomized to IH oxytocin

Group 2 – Sessions 1 and 2

Procedure	Pre-dose	Time Post Dose														
		2 min	3 min	5 min	8 min	10 min	15 min	20 min	30 min	45 min	1 hr	1.5 hr	2 hr	2.5 hr	3 hr	4 hr
Brief Physical Exam	X															
Pregnancy Test	X															
Alcohol Breath Test, Smokerlyzer, Urine Drug Screen ¹	X															
Vital signs ²	X			X			X		X		X					X
12-lead ECG	X	X					X		X	X		X				X
Cardiac Telemetry		-----Continuous-----														
Spirometry ³	X											X				
Pharmacokinetic blood sample	X ⁵	X	X	X	X	X	X	X	X	X	X	X	X	X	X	X
Immunogenicity Sample	X															
Laboratory assessments (including liver chemistries)	X															X
Prior medication review	X															
Concomitant medication review		-----continuous review-----														
AE review		-----continuous review-----														
SAE Review		-----continuous review-----														
Discharge from unit ⁴																X

1. Smokerlyzer at Principal Investigator (PI)/designee discretion if smoking history in question.
2. Includes blood pressure, heart rate, temperature, respiratory rate, and SpO₂
3. FEV 1.0 will be performed in triplicate at each time point. Record all three values on source document, and record best effort in eCRF.
4. Discharge at PI discretion, no sooner than 4-hours post-dose.
5. 3 pre-dose samples: approximately 1 hr pre-dose, 30 minutes pre-dose, and 15 minutes pre-dose

7.2. Screening and Critical Baseline Assessments

Cardiovascular medical history/risk factors (as detailed in the CRF) will be assessed at screening.

The following demographic parameters will be captured: year of birth, sex, race and ethnicity.

Medical/medication/family history will be assessed as related to the inclusion/exclusion criteria listed in Section 5.

Procedures conducted as part of the subject's routine clinical management [e.g. brief physical exam, laboratory assessments] and obtained prior to signing of informed consent may be utilized for Screening or baseline purposes provided the procedure meets the protocol-defined criteria and has been performed within the timeframe defined in the Time and Events Schedule.

7.3. Safety

Planned time points for all safety assessments are listed in the Time and Events Table (Section 7.1). Additional time points for safety tests (such as vital signs, physical exams and laboratory safety tests) may be added during the course of the study based on newly available data to ensure appropriate safety monitoring.

7.3.1. Adverse Events (AE) and Serious Adverse Events (SAEs)

The definitions of an AE or SAE can be found in [Appendix 3](#) (see Section 12.3).

The investigator and their designees are responsible for detecting, documenting and reporting events that meet the definition of an AE or SAE.

7.3.1.1. Time period and Frequency for collecting AE and SAE information

- Any SAEs assessed as related to study participation (e.g., protocol-mandated procedures, invasive tests, or change in existing therapy) or related to a GSK product will be recorded from the time a subject consents to participate in the study up to and including any follow-up contact.
- AEs will be collected from the start of Study Treatment until the follow-up contact (see Section 7.3.1.3), at the timepoints specified in the Time and Events Table (Section 7.1).
- Medical occurrences that begin prior to the start of study treatment but after obtaining informed consent may be recorded on the Medical History/Current Medical Conditions section of the CRF or appropriate source document.
- All SAEs will be recorded and reported to GSK within 24 hours, as indicated in [Appendix 3](#).
- Investigators are not obligated to actively seek AEs or SAEs in former study subjects. However, if the investigator learns of any SAE, including a death, at any

time after a subject has been discharged from the study, and she considers the event reasonably related to the study treatment or study participation, the investigator must promptly notify GSK.

NOTE: The method of recording, evaluating and assessing causality of AEs and SAEs plus procedures for completing and transmitting SAE reports to GSK are provided in [Appendix 3](#).

7.3.1.2. Method of Detecting AEs and SAEs

Care will be taken not to introduce bias when detecting AEs and/or SAEs. Open-ended and non-leading verbal questioning of the subject is the preferred method to inquire about AE occurrence. Appropriate questions include:

- “How are you feeling?”
- “Have you had any (other) medical problems since your last visit/contact?”
- “Have you taken any new medicines, other than those provided in this study, since your last visit/contact?”

7.3.1.3. Follow-up of AEs and SAEs

After the initial AE/SAE report, the investigator is required to proactively follow each subject at subsequent visits/contacts. All SAEs, and non-serious AEs of special interest (as defined in Section 4.6.1) will be followed until resolution, until the condition stabilizes, until the event is otherwise explained, or until the subject is lost to follow-up (as defined in Section 5.4). Further information on follow-up procedures is given in [Appendix 3](#).

7.3.1.4. Regulatory Reporting Requirements for SAEs

Prompt notification by the investigator to GSK of SAEs related to study treatment (even for non- interventional post-marketing studies) is essential so that legal obligations and ethical responsibilities towards the safety of subjects and the safety of a product under clinical investigation are met.

GSK has a legal responsibility to notify both the local regulatory authority and other regulatory agencies about the safety of a product under clinical investigation. GSK will comply with country specific regulatory requirements relating to safety reporting to the regulatory authority, IRB/ IEC and investigators.

Investigator safety reports are prepared for suspected unexpected serious adverse reactions according to local regulatory requirements and GSK policy and are forwarded to investigators as necessary.

An investigator who receives an investigator safety report describing a SAE(s) or other specific safety information (e.g., summary or listing of SAEs) from GSK will file it with the Investigators Brochure (IB) and will notify the IRB/IEC, if appropriate according to local requirements.

7.3.2. Adverse Events of Special Interest (AESI)

Any problem related to the delivery of the placenta or postpartum haemorrhage should be documented as an AESI using the appropriate case report form (CRF).

7.3.3. Pregnancy

Group 2 Only:

- Details of all pregnancies will be collected after the start of dosing and until follow-up.
- If a pregnancy is reported then the investigator should inform GSK within 2 weeks of learning of the pregnancy and should follow the procedures outlined in [Appendix 5](#).

7.3.4. Medical Device Incidents (Including Malfunctions)

GSK medical devices are being provided for use in this study. In order to fulfil regulatory reporting obligations worldwide the investigator is responsible for the detection and documentation of events meeting the definitions of incident or malfunction that occur during the study with such devices.

The definition of a Medical Device Incident can be found in Section [12.4](#).

NOTE: Incidents fulfilling the definition of an AE/SAE will also follow the processes outlined in Section [12.3.6](#) and [Appendix 3](#) of the Protocol.

7.3.4.1. Time Period for Detecting Medical Device Incidents

- Medical device incidents or malfunctions of the device that result in an incident will be detected, documented and reported during all periods of the study in which the GSK medical devices are available for use.
- If the investigator learns of any incident at any time after a subject has been discharged from the study, and such incident is reasonably related to a GSK medical device provided for the study, the investigator will promptly notify GSK.

NOTE: The method of documenting Medical Device Incidents is provided in [Appendix 4](#).

7.3.4.2. Follow-up of Medical Device Incidents

- All medical device incidents involving an AE will be followed until resolution of the event, until the condition stabilizes, until the condition is otherwise explained, or until the subject is lost to follow-up (as defined in Section [5.4](#)). This applies to all subjects, including those withdrawn prematurely.

- The investigator is responsible for ensuring that follow-up includes any supplemental investigations as may be indicated to elucidate as completely as practical the nature and/or causality of the incident.
- New or updated information will be recorded on the originally completed form with all changes signed and dated by the investigator.

7.3.4.3. Prompt Reporting of Medical Device Incidents to GSK

- Medical device incidents will be reported to GSK within 24 hours once the investigator determines that the event meets the protocol definition of a medical device incident.
- Facsimile transmission of the "Medical Device Incident Report Form" is the preferred method to transmit this information to the Medical Monitor or SAE coordinator.
- The same individual will be the contact for receipt of medical device reports and SAEs.
- In the absence of facsimile equipment, notification by telephone is acceptable for incidents, with a copy of the "Medical Device Incident Report Form" sent by overnight mail.

7.3.4.4. Regulatory Reporting Requirements for Medical Device Incidents

- The investigator will promptly report all incidents occurring with any GSK medical device provided for use in the study in order for GSK to fulfil the legal responsibility to notify appropriate regulatory bodies and other entities about certain safety information relating to medical devices being used in clinical studies.
- The investigator, or responsible person according to local requirements (e.g., the head of the medical institution in Japan), will comply with the applicable local regulatory requirements relating to the reporting of incidents to the IRB/IEC.

7.3.5. Physical Exams

- A brief physical examination will include, at a minimum assessments of the lungs, cardiovascular system, and abdomen (liver and spleen if palpable).
- Investigators should pay special attention to clinical signs related to previous serious illnesses

7.3.6. Vital Signs

Vital signs will be measured in semi-supine position after 5 minutes rest and will include temperature, systolic and diastolic blood pressure, pulse rate and respiratory rate (unless otherwise specified in T&E).

7.3.7. Documentation of Labour Events

The time that the following labour events occurred will be collected:

- Time of crowning
- Time of birth
- Time of delivery of placenta

7.3.8. Electrocardiogram (ECG) (Group 2 Only)

- Triplicate 12-lead ECGs will be obtained at screening as listed in Section 7.1.1.
- Single 12-lead ECGs will be obtained at each timepoint as listed in Section 7.1.2 using an ECG machine that automatically calculates the heart rate and measures PR, QRS, QT, and QTc intervals. Refer to Section 5.4.3 for QTc withdrawal criteria and additional QTc readings that may be necessary.
- At all single 12-lead ECG time-points if QTc >450, repeat twice and take average reading.

7.3.9. Continuous Cardiac Telemetry (Group 2 Only)

Continuous cardiac telemetry will be started at least 10 minutes pre-dose (to obtain a stable reading) and continue until at least the first hour after IV and IH placebo / oxytocin administration and then as deemed necessary by the investigator. Full disclosures will be reviewed in detail and the review maintained as part of the subject's source documents.

7.3.10. Device Acceptability Questionnaire (Group 1 Only)

A device acceptability questionnaire will be administered to subjects in Group 1 following use of the ROTAHALER ([Appendix 7](#)).

7.3.11. Clinical Safety Laboratory Assessments

All protocol required laboratory assessments, as required by Section 7.1 and defined in [Table 4](#), must be conducted in accordance with the Laboratory Manual, and Protocol Time and Events Schedule. Laboratory requisition forms must be completed and samples must be clearly labelled with the subject number, protocol number, site/centre number, and visit date. Details for the preparation and shipment of samples will be provided by the laboratory and are detailed in the SRM. Reference ranges for all safety parameters will be provided to the site by the laboratory responsible for the assessments.

If additional non-protocol specified laboratory assessments are performed at the institution's local laboratory and result in a change in subject management or are considered clinically significant by the investigator (e.g., SAE or AE or dose modification) the results must be recorded in the CRF.

Refer to the SRM for appropriate processing and handling of samples to avoid duplicate and/or additional blood draws.

All study-required laboratory assessments will be performed by a central laboratory, apart from:

- Tests performed as part of routine care in Group 1.

NOTE: Local laboratory results are only required in the event that the central laboratory results are not available in time for either a treatment and/or response evaluation to be performed. Additionally if the local laboratory results are used to make either a treatment or response evaluation, the results must be entered into the CRF.

Subjects in Group 1 are not required to undergo additional laboratory assessments beyond those done as part of their routine care. However, the investigator/designee may conduct any of the tests listed in [Table 4](#) in order to confirm eligibility. Haematology, clinical chemistry, and additional parameters to be tested in all Group 2 subjects are listed in [Table 4](#).

Table 4 Protocol Required Safety Laboratory Assessments

Laboratory Assessments	Parameters			
Haematology	Platelet Count	RBC Indices:		White Blood Cell (WBC) count with Differential:
	Red Blood Cell (RBC) Count	Mean Corpuscular Volume (MCV)	Neutrophils	
	Hemoglobin	Mean Corpuscular Hemoglobin (MCH)	Lymphocytes	
	Hematocrit		Monocytes	
			Eosinophils	
			Basophils	
Clinical Chemistry ¹	Blood Urea Nitrogen (BUN)	Potassium	Aspartate aminotransferase (AST) (SGOT)	Total and direct bilirubin
	Creatinine	Sodium	Alanine aminotransferase (ALT) (SGPT)	Total Protein
	Glucose	Calcium	Alkaline phosphatase	Albumin
Other Screening Tests	HIV Hepatitis B (HBsAg) Hepatitis C (Hep C antibody) Follicle Stimulating Hormone (FSH) and estradiol (as needed in women of suspected non-child bearing potential only)			

Laboratory Assessments	Parameters
	Alcohol and drug screen (to include at minimum: amphetamines, barbiturates, cocaine, opiates, cannabinoids and benzodiazepines) Serum or urine hCG Pregnancy test (Group 2 only) ²
NOTES : 1. Details of Liver Chemistry Stopping Criteria and Required Actions and Follow-Up Assessments after liver stopping or monitoring event are given in Section 12.2 and Appendix 2 2. Local urine testing will be standard for the protocol unless serum testing is required by local regulation or ethics committee.	

All laboratory tests with values that are considered clinically significantly abnormal during participation in the study should be repeated until the values return to normal or baseline. If such values do not return to normal within a period judged reasonable by the investigator, the etiology should be identified and the sponsor notified.

7.4. Pharmacokinetics

7.4.1. Blood Sample Collection

Blood samples for pharmacokinetic (PK) analysis of oxytocin will be collected at the time points indicated in Section 7.1, Time and Events Table. The actual date and time of each blood sample collection will be recorded. The timing of PK samples may be altered and/or PK samples may be obtained at additional time points to ensure thorough PK monitoring.

At each time point, 4 mL of blood will be collected into study-specific tubes formulated to further inhibit peptidase activity. Additional details regarding collection/shipping procedures are provided in the SRM.

7.4.2. Sample Analysis

Plasma analysis will be performed under the control of PTS-DMPK, GlaxoSmithKline, the details of which will be included in the SRM. Concentrations of oxytocin will be determined in plasma samples using the currently approved bioanalytical methodology. Raw data will be archived at the bioanalytical site (detailed in the SRM). Once the plasma has been analyzed for oxytocin any remaining plasma may be analysed for metabolites of oxytocin and the results reported separately.

7.5. Biomarkers

7.5.1. Pharmacodynamic Markers

Pre and post-delivery full blood counts will be collected from Group 1 subjects to assess for a change in haemoglobin levels.

7.5.2. Immunogenicity

Blood samples will be taken at the time points specified in the Time and Events Table (Section 7.1) to assess the immunogenicity of oxytocin.

Pre- and post-dose samples will be retained in the event that further immunologic tests are deemed necessary to support observations of unexpected anaphylaxis/hypersensitivity, and / or a PK profile for IH oxytocin in any Dosing Session which is regarded by the GSK Study Team to be reasonably attributable to circulating anti-oxytocin antibodies.

Details of the collection / shipping procedures are provided in the SRM.

8. DATA MANAGEMENT

- For this study subject data will be entered into GSK defined CRFs, transmitted electronically to GSK or designee and combined with data provided from other sources in a validated data system.
- Management of clinical data will be performed in accordance with applicable GSK standards and data cleaning procedures to ensure the integrity of the data, e.g., removing errors and inconsistencies in the data.
- Adverse events and concomitant medications terms will be coded using MedDRA (Medical Dictionary for Regulatory Activities) and an internal validated medication dictionary, GSKDrug.
- CRFs (including queries and audit trails) will be retained by GSK, and copies will be sent to the investigator to maintain as the investigator copy. Subject initials will not be collected or transmitted to GSK according to GSK policy.

9. STATISTICAL CONSIDERATIONS AND DATA ANALYSES

9.1. Hypotheses

The primary objective of this study is to characterize the pharmacokinetics of 400 mcg IH oxytocin and 10 I.U. IM oxytocin in women in TSL.

No formal hypotheses will be tested, however, the following comparisons are of interest, within Group 1, (IH vs. IM) and between Group 1 and Group 2 (IH oxytocin comparison in TSL vs. non-pregnant women on oral contraception) and between Cohorts A and B in

Group 2 (IH and IV oxytocin comparison in non-pregnant women in the presence and absence of oral contraceptive). For each PK endpoint of interest, point estimates and corresponding two-sided 90% confidence intervals will be constructed for the ratio of the geometric mean of the test treatment to the geometric mean of the reference treatment, $\mu(\text{test})/\mu(\text{reference})$ to provide the range of plausible values for the comparisons of interest.

9.2. Sample Size Considerations

A sufficient number of subjects will be enrolled to ensure approximately 20 evaluable subjects (10 in each of the IM and IH groups) complete all dosing and critical assessments in Group 1, as well as 5 subjects in each cohort in Group 2. Whilst sample size is based on feasibility, precision calculation was also done to approximate the estimate of the expected half width of 90% CI around point estimate for the main comparison of interest (IH oxytocin to 10 I.U. IM oxytocin in women in TSL) using a t-test.

Table 5 illustrates the associated 90% CIs for the mean treatment ratios, assuming between subject SDs of 0.424 and 0.601 (SDs are based on log transformed data) for AUC (0-3h) and Cp10 respectively, for the comparisons of interest detailed in Section 9.1. Calculations are based on a symmetric two-tailed procedure on the loge scale and a type I error rate of 10%. These values represent estimates of the between-subject variability observed in the FTIH study 201558 [GlaxoSmithKline Document Number 2016N277949_00].

Table 5 Estimated 90% Confidence Intervals for Treatment Ratios

N	Parameter	Between Subject Standard Deviation (SD)	Estimated Treatment Ratio	Precision	Expected 90% CI
10	AUC(0-3h)	0.424 (CVb=44.35%)	1	38.30%	(0.72, 1.38)
10	Cp10	0.601 (Cvb=65.96%)	1	58.20%	(0.63,1.58)

The precision estimates are deemed acceptable to assess the study objectives at this stage of development.

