3.2. Group 2: Non-pregnant, non-lactating females of child bearing potential

Objectives	Endpoints
Primary	

 To evaluate the safety and tolerability of IH and IV oxytocin. 	
 General safety parameters: adverse events; absolute values and changes over time of vital signs (blood pressure, heart rate) and 12-lead electrocardiogram (ECG) parameters (PR, QRS, QT, Corrected QT interval [QTc] intervals) from pre-dose values. Specific respiratory safety parameters: adverse respiratory events as monitored by spirometry including Forced expiratory volume at 1 minute (FEV1.0), respiratory rate, and pulse oximetry.

 To characterize the pharmacokinetics of single doses of IH oxytocin and 5 I.U. IV oxytocin. 	
 Plasma concentration time profile for IH oxytocin and 5 I.U. IV oxytocin. PK parameters: C_{max}, C_{p10}, C_{p20}, C_{p30}, t_{max}, AUC, Plasma clearance (CL), volume of distribution and t_{1/2} will be calculated as data permit.
Exploratory	

 To evaluate endogenous plasma oxytocin concentrations in non-pregnant females in the presence and absence of the combined oral contraceptive. 	
 Pre-dose plasma concentrations of oxytocin.

 To compare the IH pharmacokinetics of oxytocin between Cohort A (subjects on combined oral contraceptive) and Cohort B (subjects using a non-hormonal form of contraception). 	
 C_{p10}, C_{p20}, C_{p30}, C_{max}, AUC(0-3h), Area under the concentration-time curve from time zero to infinity (AUC[0-∞]) and t_{1/2}, will be compared as data permit.

 To compare the IV pharmacokinetics of oxytocin between Cohort A and Cohort B. 	
 C_{max}, AUC, t_{1/2}, CL and Volume of distribution (VOD) will be compared as data permit.

[figure not shown]
3.3. Groups 1 and 2: Women in TSL and Non-pregnant, non-lactating females of child bearing potential

Objectives	Endpoints
Exploratory	

 To compare pharmacokinetics of IH oxytocin between Group 1 and Group 2. 	
 Cp10, Cp20, Cp30, Cmax, AUC(0-3h) AUC(0-∞), and t1/2 will be compared as data permit.

[figure not shown]

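### Protocol Section 9.2 contradicts itself on what Table 5 covers: its 10 vs 10 precision is attributed to every Section 9.1 comparison, but two of the three are planned at 10 vs 5 and 5 vs 5

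*Protocol*

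**What the plan says.** Section 9.1 names three comparisons of interest. The first is IH vs IM within Group 1. The second is between groups: "IH oxytocin comparison in TSL vs. non-pregnant women on oral contraception", which means Cohort A. The third is Cohort A vs Cohort B: "IH and IV oxytocin comparison in non-pregnant women in the presence and absence of oral contraceptive".

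Section 9.2 plans 10 evaluable women in each Group 1 arm, "as well as 5 subjects in each cohort in Group 2". It bases the sample size on feasibility and says that the precision calculation was done "for the main comparison of interest (IH oxytocin to 10 I.U. IM oxytocin in women in TSL) using a t-test". The following sentence introduces Table 5, whose only N is 10, as showing the 90% intervals "for AUC (0-3h) and Cp10 respectively, for the comparisons of interest detailed in Section 9.1". Table 5 gives 38.30% (0.72, 1.38) for AUC(0-3h) and 58.20% (0.63, 1.58) for Cp10. The section closes: "The precision estimates are deemed acceptable to assess the study objectives at this stage of development".

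Table 6 in Section 9.2.1 has N=5 rows: 61.90% (0.61, 1.61) at a CV of 44.35%, and 98.00% (0.50, 1.98) at 65.96%. The text labels Table 6 as scenarios for IH vs IM in Group 1.

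**The concern.** Two adjacent sentences give Table 5 different scopes, and only the narrower one can be right. Under the wider one, the protocol claims for the between-group and between-cohort comparisons a precision that their planned numbers do not deliver. The acceptability statement then covers those comparisons too, since they are listed objectives in Sections 3.2 and 3.3.

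The cohort comparison matters most. Section 2.1 says that the two cohorts will help to assess whether future studies need women to be on an oral contraceptive. The conclusion hoped for there is that the cohorts are alike, and the width of the interval determines how much such a conclusion is worth.

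**Working it through.** **Inputs**, all from Protocol Sections 9.1 and 9.2. The between-subject SD on the log scale is 0.424 for AUC(0-3h) and 0.601 for Cp10, from study 201558. The interval is a two-sided 90% t interval. Planned sizes are 10 per Group 1 arm and 5 per Group 2 cohort. The SDs agree with the printed CVs: √ln(1 + 0.4435²) = 0.424 and √ln(1 + 0.6596²) = 0.601.

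**Formula.** With df = n1 + n2 − 2, the log-scale half width is

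h = t(0.95, df) × SD × √(1/n1 + 1/n2).

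The expected half width multiplies h by c4(df) = √(2/df) × Γ((df+1)/2) / Γ(df/2), because the sample SD will on average fall slightly below the true one. Precision is exp(h) − 1, and the interval at a ratio of 1 is exp(−h) to exp(h).

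**Step 1: reproduce Table 5.** For 10 vs 10, df = 18 and c4 = 0.9862.
- AUC(0-3h): plain h = 0.3288, or 38.9%. With c4 it is 38.3% (0.72, 1.38). Stated: 38.30% (0.72, 1.38).
- Cp10: plain h = 0.4661, or 59.4%. With c4 it is 58.4% (0.63, 1.58). Stated: 58.20% (0.63, 1.58).

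Table 5 is therefore a calculation with 10 subjects in each of two groups. The N=5 rows of Table 6 reproduce in the same way as 5 vs 5: 62.2% and 98.4% with c4, against 61.90% and 98.00% printed.

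**Step 2: same SDs and method at the planned sizes, IH only.** Main figures use c4; plain-t precision is in square brackets.

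| Comparison | Sizes | AUC(0-3h) | Cp10 |
|---|---|---|---|
| Group 1 IH vs IM | 10 vs 10 | 38.3% (0.72, 1.38) [38.9%] | 58.4% (0.63, 1.58) [59.4%] |
| Group 1 IH vs Cohort A IH | 10 vs 5 | 49.7% (0.67, 1.50) [50.9%] | 77.2% (0.56, 1.77) [79.1%] |
| Cohort A IH vs Cohort B IH | 5 vs 5 | 62.2% (0.62, 1.62) [64.7%] | 98.4% (0.50, 1.98) [102.8%] |

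**Step 3: relative width on the log scale** (plain t, AUC). For 10 vs 5: 0.4113 / 0.3288 = 1.25, about 25% wider. For 5 vs 5: 0.4987 / 0.3288 = 1.52, about 50% wider.

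**Sensitivity.** If the variance were pooled over all three IH groups (10, 5 and 5 women; df = 17), plain t gives 49.8% and 77.3% for 10 vs 5, and 59.4% and 93.7% for 5 vs 5. The conclusion does not change.

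**The case against.** The strongest reply is that an attentive reader will not be misled. The limiting sentence stands directly before the broad one, Table 5 prints N=10, and the same paragraph gives 5 per cohort. The 5 vs 5 widths are already in Table 6; they carry a Group 1 label, but the same SDs and N give the same width. The affected comparisons are exploratory, no hypothesis is tested, the sample size rests on feasibility, and each comparison will be reported with its own 90% interval.

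All of that is true, and it makes the point modest. It does not remove the contradiction or narrow the acceptability statement, and no table gives a 10 vs 5 figure.

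Some stronger readings are not supported:
- A reader might infer that Table 5 is miscalculated. It is not; it reproduces for 10 vs 10.
- A reader might call both other comparisons far less precise. That suits 5 vs 5; the loss at 10 vs 5 is moderate.
- A reader might see a conflict between the Section 3.3 objective, "To compare pharmacokinetics of IH oxytocin between Group 1 and Group 2", and the use of Cohort A alone. Sections 9.1 and 9.4.3.1 both specify women on the contraceptive, and Section 4.4 explains why Cohort A is the control. This makes a general objective specific, and analysing all of Group 2 would be a preference.
- A reader might think that the contraceptive question turns on a Cp10 ratio. Section 2.1 asks mainly about endogenous oxytocin levels, which Table 5 does not address, and no decision rule uses that ratio.

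**Conclusion.** The point holds as an internal contradiction with a misattributed precision. Table 5 describes Group 1 IH vs IM only. For IH at the planned sizes, AUC(0-3h) and Cp10 precision is about 50% and 77% for Group 1 vs Cohort A, and about 62% and 98% for Cohort A vs B, against the stated 38.3% and 58.2%. With an estimated Cp10 ratio of 1, the cohort comparison would rule out only differences of about two-fold or more, where Table 5 suggests about 1.6-fold.

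These figures assume that the study 201558 SDs apply equally to women in the third stage of labour and to both cohorts, and that every planned subject is evaluable. They do not extend to IV. Study 201558 gave IH and IM but not IV (Section 2.2.1), so the protocol offers no SD for the IV part of the cohort comparison, and the IV cohort endpoints in Section 3.2 do not include Cp10.

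Nothing here shows that the sample size is inadequate for an exploratory, feasibility-based comparison.

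**What to change.** In Section 9.2, limit the sentence introducing Table 5, and the closing acceptability statement, to IH vs IM in Group 1.

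Add the IH precision for Group 1 vs Cohort A at 10 vs 5: about 50% (0.67, 1.50) for AUC(0-3h) and 77% (0.56, 1.77) for Cp10. For Cohort A vs B, refer to the N=5 rows already in Table 6 (61.90% and 98.00%) and widen that table's description to match. Quoting those rows avoids printing two slightly different 5 vs 5 values in one section.

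Mark both as IH only, note that no SD is given for IV, and say that the exploratory cohort comparison can exclude only Cp10 differences of about two-fold or more.

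The cost is a text edit with no added subjects. The downside is that the stated precision for the exploratory comparisons becomes less favourable.
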